### **9.3 Final Evaluations, Off Treatment (within 7 days of last treatment)**

At the completion of all follow-up evaluations, the Off Protocol Treatment Summary Form should be completed in AdvantageEDC.

- 9.3.1 Complete medical history and physical examination. To include vital signs, weight, performance status, adverse event evaluation)
- 9.3.2 CBC with differential and platelets, serum chemistry, and LFTs defined in [9.1.3](#).
- 9.3.3 CD4+ and CD8+ lymphocyte counts and HIV viral load
- 9.3.4 Serum TSH, amylase, lipase

- 9.3.5 PT/INR and PTT
- 9.3.6 Urine dipstick or urinalysis. Proteinuria seen on urine dipstick or UA should warrant urine protein/creatinine ratio (UPCR) determination and management according to [Section 6.1.9](#).
- 9.3.7 Electrocardiogram (ECG) and QTc assessments
- 9.3.8 CT scan for tumor measurement. Radiologic documentation must be provided for participants removed from study for progressive disease. Participants with cutaneous Kaposi sarcoma will not require CT scans and will be evaluated for response according to [Section 11.2](#). Chest x-ray will be performed as clinically indicated.
- 9.3.9 Collect diary upon completion.

#### **9.4 Final Evaluations, Off Study**

At the completion of all follow-up evaluations, the Off Study Summary Form should be completed in AdvantageEDC.

Participants will be followed for 30 days ( $\pm 3$  days) from the date of study treatment discontinuation or until toxicity resolution, whichever is later. Toxicity resolution may be monitored by the local site personnel via telephone contact with the participant.

## 10.0 BIOMARKER, CORRELATIVE, AND SPECIAL STUDIES

### 10.1 Biomarker Studies

10.1.1 To investigate possible pharmacokinetic interactions between cabozantinib and antiretroviral therapy in persons with HIV infection.

This study will enroll participants with HIV infection across three Strata based on current antiretroviral regimen (Ritonavir or Cobicistat (CYP3A4 inhibitor)-containing HAART [**Stratum A**]; Efavirenz or Etravirine (CYP3A4 inducer)-containing HAART [**Stratum B**]; and Others [**Stratum C**]). The study therefore provides an opportunity to evaluate possible pharmacokinetic interactions between cabozantinib and antiretroviral therapies.

Pharmacokinetic (PK) sampling studies are proposed for all participating participants on the study to assess cabozantinib pharmacokinetics (total and possibly unbound concentrations of parent drug and relevant metabolites). In addition, when feasible, samples will be requested from the participant at the time of disease progression and in the event of DLT or other persistent and severe toxicity. Evaluations will occur at steady-state (Cycle 1, Days 22/23) given the long half-life of the drug ( $91.3 \pm 33.3$  hr) which is not conducive to a comprehensive assessment after a single dose. If a participant misses a dose of cabozantinib during Cycle 1 prior to Cycle 1 Days 22/23 and will continue on treatment, [name] should be contacted to determine the optimal timing of the PK collection, which may no longer occur on Cycle 1 Days 22/23. Since cabozantinib is to be administered continuously, the adjustment may occur in the date of the collection but not the 8 samples to be obtained. The exact timing will depend on the duration of interruption and proximity to Cycle 1 Days 22/23. In some circumstances, the PK collection may be waived due to difficulties in rescheduling the PK.

**To permit pharmacokinetic sampling studies, AM dosing is required during the first cycle of therapy.** Blood samples will be collected prior to the initial AM cabozantinib dose and at 4 hours post-dose on Cycle 1 Day 1. Blood sampling for steady-state PK determinations will be collected during the dosing interval at pre-dose (Cycle 1, Day 22), 0.5, 1, 2, 4, 6, 8, and 24 hr (Cycle 1, Day 23). For the optional samples that are to be obtained at the time of disease progression or in the event of toxicity, a blood sample should be drawn as close as possible to the time of the event with documentation of the last cabozantinib dose administered. For each sample, at least 6 mL of whole blood will be collected in tubes or Vacutainers™ containing EDTA as an anticoagulant, kept on ice, and centrifuged within 30 min to isolate plasma. Plasma will be frozen in two to three aliquots immediately and stored at  $-70^{\circ}\text{C}$  (or less) protected from light for later analysis by the Analytical Pharmacology Core Laboratory at the Sidney Kimmel Comprehensive Cancer Center at Johns Hopkins University under the direction of [name] (See [Appendix IV](#) Pharmacokinetic (PK) Specimen Collection, Preparation and Shipping Instructions).

Samples will be measured using liquid chromatography/tandem mass spectrometric (LC/MS/MS) method in the Analytical Pharmacology Core

Laboratory at the Sidney Kimmel Comprehensive Cancer Center (SKCCC) at Johns Hopkins. Relevant individual PK parameters will be estimated using non-compartmental or compartmental PK methods with the software WinNonlin. For each Stratum, the pharmacokinetic variables will be tabulated and descriptive statistics (e.g., geometric means and coefficients of variation) calculated for each dose level. Pharmacokinetic parameters (i.e.,  $T_{1/2}$ ,  $Cl$ , and AUC) will be compared across relevant antiretroviral therapies using nonparametric statistical testing techniques. Correlations with toxicity and efficacy will be explored using nonparametric statistical testing techniques. Significance for comparisons will be at the  $p<0.05$  level.

10.1.2 To investigate the effects of therapy on participant immune status and HIV viral load.

This trial will include participants with HIV infection, provided participants are receiving appropriate treatment and followed by physicians monitoring their care. While it is not anticipated that cabozantinib will alter immune reconstitution in participants, HIV viral load and CD4+ cell counts will be monitored to ensure adequate control of the participant's HIV infection. Samples will be obtained locally at baseline, at time of Pharmacokinetic (PK) Specimen Collection on Cycle 1, Day 22, and at 12 week intervals while on study therapy, and at time of study discontinuation.

## 10.2 Laboratory Correlative Studies

10.2.1 To investigate possible pharmacokinetic interactions between cabozantinib and antiretroviral therapy in persons with HIV infection.

### 10.2.1.1 Collection of specimens

This study will be performed on all participating participants as described in [Appendix IV](#), Pharmacokinetic (PK) Specimen Collection, Preparation and Shipping Instructions. Samples will be collected prior to the initial cabozantinib dose and at 4 hours post-dose on Cycle 1 Day 1. Steady-state PK samples will be collected during the dosing interval at pre-dose (Cycle 1, Day 22), 0.5, 1, 2, 4, 6, 8, and 24 hr (Cycle 1, Day 23). Day 22 and Day 23 PK samples may be collected  $\pm$  1 day. If a participant misses a dose of cabozantinib during Cycle 1 prior to Cycle 1 Days 22/23 and will continue on treatment, [name] should be contacted to determine the optimal timing of the PK collection, which may no longer occur on Cycle 1 Days 22/23. In addition, when feasible, samples will be requested from the participant at the time of disease progression and in the event of DLT or other persistent and severe toxicity.

### 10.2.1.2 Handling of specimens

Specimens will be obtained from the local site as described in [Appendix IV](#), Pharmacokinetic (PK) Specimen Collection, Preparation, and Shipping Instructions.

#### 10.2.1.3 Shipping of specimens

These studies will be performed in an AMC-designated Pharmacology Core Laboratory. Specimens will be prepared and shipped from the local site as described in [Appendix IV](#), Pharmacokinetic (PK) Specimen Collection, Preparation, and Shipping Instructions.

#### 10.2.1.4 Sites performing correlative study

All participating sites.

### 10.2.2 To investigate the effects of therapy on participant immune status and HIV viral load.

#### 10.2.2.1 Collection of specimens

All participants will have baseline and follow-up evaluations of CD4+ and CD8+ lymphocyte counts and HIV viral load on Cycle 1, Day 22 (along with Pharmacokinetic (PK) Specimen collection) and at every 12 weeks during study participation as part of standard HIV care. Participants will also have these evaluations performed at time of study discontinuation.

#### 10.2.2.2 Handling of specimens

Testing will be performed locally.

#### 10.2.2.3 Sites performing correlative study

All participating sites.

## 11.0 MEASUREMENT OF EFFECT

Although response is not the primary endpoint of this trial, participants with measurable disease will be assessed by standard criteria. For the purposes of this study, participants should be re-evaluated every  $8 \pm 1$  weeks. In addition to a baseline scan, confirmatory scans will also be obtained at least 4 weeks following initial documentation of an objective response. **Participants with solid tumors other than Kaposi sarcoma will be followed for response according to [Section 11.1](#), and participants with Kaposi sarcoma will be followed for response according to [Section 11.2](#).**

### 11.1 Antitumor Effect – Solid Tumors

For the purposes of this study, participants should be re-evaluated for response every 8 weeks. In addition to a baseline scan, confirmatory scans should also be obtained not less than 4 weeks following initial documentation of objective response.

Response and progression will be evaluated in this study using the new international criteria proposed by the revised Response Evaluation Criteria in Solid Tumors (RECIST) guideline (version 1.1) [Eur J Ca 45:228-247, 2009]. Changes in the largest diameter (unidimensional measurement) of the tumor lesions and the shortest diameter in the case of malignant lymph nodes are used in the RECIST criteria.

#### 11.1.1 Definitions

Evaluable for toxicity: All participants will be evaluable for toxicity from the time of their first treatment with cabozantinib (XL184).

Evaluable for objective response: Only those participants who have measurable disease present at baseline, have received at least one cycle of therapy, and have had their disease re-evaluated will be considered evaluable for response. These participants will have their response classified according to the definitions stated below. (Note: Participants who exhibit objective disease progression prior to the end of cycle 1 will also be considered evaluable.)

Evaluable non-target disease response: Participants who have lesions present at baseline that are evaluable but do not meet the definitions of measurable disease, have received at least one cycle of therapy, and have had their disease re-evaluated will be considered evaluable for non-target disease. The response assessment is based on the presence, absence, or unequivocal progression of the lesions.

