#### **5.4 Duration of Therapy**

In the absence of treatment delays due to adverse event(s), treatment may continue until one of the following criteria applies:

- Disease progression,
- Intercurrent illness that prevents further administration of treatment,
- Dose-limiting toxicity (DLT requiring discontinuation of therapy, as defined in [Section 5.2](#)). Dose reductions in the first cycle of therapy for cabozantinib-related adverse events are permitted.
- Other unacceptable adverse event(s),
- Treatment delay of 14 days or greater during Cycle 1 due to unresolved toxicity (DLT definition, [Section 5.2](#)).
- Treatment delay in subsequent cycles > 6 weeks due to toxicity (treatment delays for other reasons may be permitted at the discretion of the Study Chairs),
- Participant decides to withdraw from the study.
- General or specific changes in the participant's condition render the participant unacceptable for further treatment in the judgment of the investigator, including:
  - Necessity for treatment with other anticancer treatment prohibited by the protocol.
  - Change to a ritonavir or cobicistat-containing antiretroviral regimen for a participant enrolled on a different study arm (see [Section 5.3.1.2](#)).
  - Sexually active participants who refuse to use medically accepted barrier methods of contraception (e.g., male condom, female condom) during the course of the study and for 6 months following discontinuation of study treatment.
  - Women who become pregnant or are breastfeeding.
- Request by regulatory agencies for termination of treatment of an individual participant or all participants under the protocol.
- Significant noncompliance with the protocol schedule in the opinion of the investigator.
- The minimum dose of study treatment for Stratum A will be the Dose Level -1 dose, and the lowest dose of study treatment for Stratum B and Stratum C will be the Dose Level -2 dose. Participants who cannot tolerate the lowest Dose Level dose for the specified study Stratum will have study treatment discontinued.

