### **12.4 Analysis of Secondary Endpoints**

Secondary endpoints for this study include response rates and effects of therapy on HIV viral load and CD4+ and CD8+ cell counts, as well as the results of pharmacokinetic studies. For participants with measurable disease, response evaluations will occur at 2 cycle intervals via RECIST 1.1. Study treatment may continue indefinitely until one of the following criteria applies: 1) unacceptable toxicity (including DLT in cycle 1); 2) progressive disease; or 3) participant withdrawal or removal.

To investigate possible pharmacokinetic interactions between cabozantinib and antiretroviral therapy in persons with HIV infection, pharmacokinetic analysis calculations will be conducted using WinNonlin (Pharsight Corporation, Mountain View, CA) with noncompartmental or compartmental methods. Relevant pharmacokinetic parameters will be computed for cabozantinib and relevant metabolites. The pharmacokinetic variables will be tabulated and descriptive statistics (e.g., geometric means and coefficients of variation) calculated for each dose level. Pharmacokinetic parameters (i.e.,  $T_{1/2}$ , Cl, and AUC) will be compared across relevant antiretroviral therapies using nonparametric statistical testing techniques. Concentrations obtained from the time of disease progression and the time of a DLT or other persistent and severe toxicity will be treated as independent samples and summarized in a descriptive manner. Correlations with toxicity and efficacy will be assessed using nonparametric statistical testing techniques. Significance for comparisons will be at the  $p<0.05$  level.

To investigate the effects of cabozantinib on participant immune status and HIV viral load, trends in CD4+ and CD8+ counts and viral load determinations during trial participation will be evaluated. A repeated measures analysis of variance will be used to assess the effect of cabozantinib on CD4+ and CD8+ cell counts and HIV viral loads across time points. Analyses will be done per stratum, where the data are sufficient. If the data do not meet the assumptions of normality, Friedman's test, the nonparametric analogue to a repeated measures analysis of variance, will be used.

Collectively and over each stratum, binomial proportions and their 95% confidence intervals will be used to preliminarily assess response rates for single agent cabozantinib in malignancies for which at least 4 participants have been enrolled.

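### The only response-evaluable set defined for solid tumours omits treated participants who stop in cycle 1 without objective progression or are never re-evaluated, and Section 12.4 names no other denominator

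*Combined protocol and SAP*

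**What the plan says.** Section 11.1.1 defines two sets that matter here. For toxicity, every participant counts from the first dose. For objective response, the set is restricted to participants with measurable disease at baseline who "have received at least one cycle of therapy, and have had their disease re-evaluated will be considered evaluable for response". A note adds one exception: "Participants who exhibit objective disease progression prior to the end of cycle 1 will also be considered evaluable".

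Section 12.4 gives the analysis: "binomial proportions and their 95% confidence intervals will be used to preliminarily assess response rates", overall and by stratum, "in malignancies for which at least 4 participants have been enrolled". It does not say which participants form the denominator, or how a participant with no post-baseline assessment is counted.

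Section 11.0 sends Kaposi sarcoma to Section 11.2, which gives response criteria but no evaluable set.

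**The concern.** The conditions in Section 11.1.1 are joined by *and*, so a participant must both complete a cycle and be re-evaluated. Someone who leaves in cycle 1 because of toxicity, clinical decline, death without imaging or withdrawal has had the drug and usually has no response to show, yet is not counted. The set is thus conditioned on tolerating treatment for 28 days.

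The exclusion may also be uneven. Toxicity is expected to vary with dose and antiretroviral stratum, and Section 12.4 reports rates by stratum, so a stratum with more early toxicity could lose more non-responders.

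At stake are the tumour-specific rates that Section 2.6.3 wants as a preliminary signal of activity. They may rest on as few as four enrolled participants, where one exclusion visibly moves the estimate.

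**Working it through.** **The plan's own figure.** Section 12.2 expects 4 to 18 participants in Stratum A, 6 to 18 in B and 6 in C. The sums 4 + 6 + 6 = 16 and 18 + 18 + 6 = 42 reproduce the stated total of 16 to 42. This figure does not depend on response. The plan states no expected response rate, excluded share, or response hypothesis.

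**Step 1: who is in the set.** Applying Section 11.1.1 to treated participants with measurable disease:

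| Course | Evaluable? | Basis |
|---|---|---|
| Objective progression before the end of cycle 1 | Yes | Exception in 11.1.1 |
| Stops in cycle 1 for toxicity, no objective progression, off-treatment CT done | No | One-cycle condition fails |
| Stops in cycle 1 through symptomatic deterioration, unimaged death or withdrawal, no objective progression | No | One-cycle condition fails |
| Completes cycle 1, stops later, off-treatment CT done | Yes | Both conditions met (9.3.8, Appendix I) |
| Completes cycle 1, never re-evaluated | No | Second condition fails |
| DLT in cycle 1, continues on a reduced dose, completes the cycle, re-evaluated | Yes | 5.4 and 6.0 allow continuation |

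**Step 2: effect on the rate.** Let N be the treated participants with measurable disease, d those excluded and x the responders, all among the N-d retained. The evaluable-set rate is x/(N-d) and the all-treated rate is x/N. Their ratio is N/(N-d) = 1/(1 - d/N). The excluded share d/N is an assumption, shown from 5% to 30%. One point in that range is 1/6, the largest DLT share that Section 5.2 allows at the MTD, if every such participant stopped without objective progression.

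| Assumed d/N | Factor | An assumed all-treated rate of 20% is reported as |
|---|---|---|
| 5% | 1/0.95 = 1.05 | 21.1% |
| 10% | 1/0.90 = 1.11 | 22.2% |
| 1/6 | 6/5 = 1.20 | 24.0% |
| 30% | 1/0.70 = 1.43 | 28.6% |

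**Step 3: groups of the size the plan expects.** Illustrative counts with exact Clopper-Pearson 95% intervals:

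| All treated | Evaluable set |
|---|---|
| 1/4 = 25.0% (0.6 to 80.6) | 1/3 = 33.3% (0.8 to 90.6) |
| 2/6 = 33.3% (4.3 to 77.7) | 2/5 = 40.0% (5.3 to 85.3) |
| 2/12 = 16.7% (2.1 to 48.4) | 2/10 = 20.0% (2.5 to 55.6) |
| 8/42 = 19.0% (8.6 to 34.1) | 8/38 = 21.1% (9.6 to 37.3) |
| 0/4 = 0% (upper limit 60.2) | 0/3 = 0% (upper limit 70.8) |

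The 42 row supposes that all 42 have measurable disease, which Section 3.1 does not require. The last row shows that without a responder only the interval changes.

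**Step 4: effect of the exception.** Take 12 treated, 2 responders and 3 who leave in cycle 1. The reported rate is 2/9 = 22.2% if none of the 3 has objective progression, 2/10 = 20.0% if one has, 2/11 = 18.2% if two have, and 2/12 = 16.7% (no inflation) if all three have.

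**The case against.** The strongest reply is that Section 12.4 never says the evaluable set is the denominator, so the inflation is inferred. That is correct. But it is the only response set defined for solid tumours other than Kaposi sarcoma, and if another was meant, its absence is itself a gap.

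A reader might infer more than the text supports:

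- **That everyone who stops before the first 8-week scan is lost.** Section 9.3.8 and Appendix I call for tumour measurement at treatment discontinuation, so a participant who stops after cycle 1 and has that CT stays evaluable. The table notes in Section 11.1.4.3 also ask sites to try to document objective progression after symptomatic deterioration. Neither point helps a cycle 1 toxicity stop without progression.
- **That every cycle 1 DLT is an exclusion.** Section 5.4 says: "Dose reductions in the first cycle of therapy for cabozantinib-related adverse events are permitted", and Section 6.0 agrees. The Synopsis and Section 12.4 read differently, listing a cycle 1 DLT among the toxicities that end treatment. How many drop out depends on which reading is followed.
- **That every tumour-specific rate is biased upward.** Groups with no responders or no exclusions keep their point estimate, and the Section 11.1.1 set does not govern Kaposi sarcoma.
- **That the threshold in Section 12.4 contradicts Section 11.1.1.** It does not. The threshold decides which malignancies are reported, and the definition decides who can be classified. A group with 4 enrolled reported on 3 satisfies both, though it is an awkward pairing.

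It is also fair that response is secondary, descriptive and preliminary, and that the paired intervals in small groups overlap almost entirely. This limits the importance of the point. It does not justify leaving the denominator unstated.

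**Conclusion.** The point holds in limited form. Section 11.1.1 leaves out treated participants with measurable disease who stop in cycle 1 without objective progression, and those never re-evaluated. Because Section 12.4 names no denominator, that set is the likely one for solid tumours other than Kaposi sarcoma.

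Where a group has at least one responder and one exclusion, its rate rises by the factor N/(N-d): 1.05 to 1.43 over the assumed 5% to 30%, and from 25% to 33% in the smallest reportable group with one exclusion and one responder.

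This rests on two assumptions: that the evaluable set is used, and that those excluded are non-responders. The documents give no excluded share, so the actual size cannot be derived. A claim of a known, general upward bias would go too far. No dose decision, MTD or enrolment figure is affected.

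**What to change.** 1. In Sections 11.1.1 and 12.4, make the main response denominator all participants who received at least one dose and had measurable disease at baseline, or Kaposi sarcoma assessable under Section 11.2. Count those without a post-baseline assessment as non-responders.
2. Report the evaluable-set rate as a labelled supportive analysis, with the number excluded and the reasons, by stratum and malignancy.
3. Apply the threshold of four to the main denominator.
4. Separately, reconcile the Synopsis (Duration), Sections 5.4 and 6.0, and Section 12.4 on whether a cycle 1 DLT ends treatment.

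No new data or procedures are needed. The cost is amended wording, which Section 14.2 makes a written amendment needing CTEP, investigator and IRB approval, and slightly lower reported rates. It could be carried with the next amendment.

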#### 11.1.2 Disease Parameters

Measurable disease: Measurable lesions are defined as those that can be accurately measured in at least one dimension (longest diameter to be recorded) as  $\geq 20$  mm by chest x-ray or as  $\geq 10$  mm with CT scan, MRI, or calipers by clinical exam. All tumor measurements must be recorded in millimeters (or decimal fractions of centimeters).

**Note:** Tumor lesions that are situated in a previously irradiated area may not be considered measurable.

**Malignant lymph nodes**: To be considered pathologically enlarged and measurable, a lymph node must be  $\geq 15$  mm in short axis when assessed by CT scan (CT scan slice thickness recommended to be no greater than 5 mm). At baseline and in follow-up, only the short axis will be measured and followed.

**Non-measurable disease**: All other lesions (or sites of disease), including small lesions (longest diameter  $< 10$  mm or pathological lymph nodes with  $\geq 10$  to  $< 15$  mm short axis), are considered non-measurable disease. Bone lesions, leptomeningeal disease, ascites, pleural/pericardial effusions, lymphangitis cutis/pulmonitis, inflammatory breast disease, and abdominal masses (not followed by CT or MRI), are considered as non-measurable.

**Note:** Cystic lesions that meet the criteria for radiographically defined simple cysts should not be considered as malignant lesions (neither measurable nor non-measurable) since they are, by definition, simple cysts.

‘Cystic lesions’ thought to represent cystic metastases can be considered as measurable lesions, if they meet the definition of measurability described above. However, if non-cystic lesions are present in the same participant, these are preferred for selection as target lesions.

**Target lesions**: All measurable lesions up to a maximum of 2 lesions per organ and 5 lesions in total, representative of all involved organs, should be identified as **target lesions** and recorded and measured at baseline. Target lesions should be selected on the basis of their size (lesions with the longest diameter), be representative of all involved organs, but in addition should be those that lend themselves to reproducible repeated measurements. It may be the case that, on occasion, the largest lesion does not lend itself to reproducible measurement in which circumstance the next largest lesion which can be measured reproducibly should be selected. A sum of the diameters (longest for non-nodal lesions, short axis for nodal lesions) for all target lesions will be calculated and reported as the baseline sum diameters. If lymph nodes are to be included in the sum, then only the short axis is added into the sum. The baseline sum diameters will be used as reference to further characterize any objective tumor regression in the measurable dimension of the disease.

**Non-target lesions**: All other lesions (or sites of disease) including any measurable lesions over and above the 5 target lesions should be identified as **non-target lesions** and should also be recorded at baseline. Measurements of these lesions are not required, but the presence, absence, or in rare cases unequivocal progression of each should be noted throughout follow-up.

